Title: Postoperative Activity Restrictions in Children (PARC)

NCT04145895

Protocol approval date: 10/29/2021

Title: Postoperative Activity Restrictions in Children (PARC)

Principal Investigator: [name]

NCT04145895

Protocol approval date: 10/29/2021

IRB# 2019-224

SUMMARY

BACKGROUND: Currently, there are no evidence-based guidelines for postoperative activity restrictions in routine pediatric surgery. Recent studies suggest that patients may return to normal activity earlier than previously thought. We aim to compare time to full activity and post-operative outcomes. This study will describe family preferences for self-directed activity restrictions (SDAR) and physician directed activity restrictions (PDAR) following routine surgeries.

STUDY DESIGN: Single institution, prospective clinical trial (NCT04145895). Patients who present for a routine inguinal hernia repair or laparoscopic appendectomy for uncomplicated appendicitis are eligible for participation. Participating families will choose to enroll in either the control (PDAR) or experimental (SDAR) groups. The PDAR patients are restricted from full activity for two weeks post-operatively. For SDAR, patients are instructed to return to full activity when pain is improving and the family feels comfortable. At 4-6 weeks postoperatively, caregivers will complete a survey to assess time to resume full activity, time to return to school and work, surgical complications, and patient and caregiver satisfaction.

BACKGROUND AND SIGNIFICANCE

Postoperative activity restrictions (PAR) serve to minimize the risk of complications and prevent stress on the operative site following abdominal surgery. By minimizing intra-abdominal pressure, PAR are used to prevent the breakdown of the surgical repair and closure.¹ Commonly restricted activities include heavy lifting, exercise, and strenuous activity. As children are highly active by nature, limiting physical activity is difficult.² Pediatric surgeons may restrict time to return to school or extracurricular activities. However, these restrictions create a societal burden through school absences and missed work days. Additionally, PAR can negatively impact a child's psychosocial well-being and cause undue family stress.²

[figure not shown]

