This study was approved by the Beaumont Institutional Review Board (2019-224). Patients who presented to Beaumont Royal Oak and Beaumont Troy for a routine inguinal hernia repair (ages 2-13 years) or laparoscopic appendectomy for uncomplicated appendicitis (ages 0-17 years) were eligible for participation. Patients meeting eligibility criteria (**Figure 1**) were identified by the pediatric surgeons, including the Primary Investigator ([name]), and were provided with an information sheet detailing the study, which served as consent for participation. Parents and patients who elected to participate then chose to enroll in the control group (PDAR) or experimental group (SDAR). The PDAR instructions detailed that patients are restricted from full, normal activity for 2 weeks after their procedure. The SDAR instructions specified that they may return to full activity when their pain is improving and the parent, or guardian, feels comfortable advancing their activity. Enrollment is still accruing for this study.

Figure 1. Patient eligibility criteria**Figure 1.** Patient eligibility criteria for participation in the clinical trial.

Data Collection

Baseline characteristics, comorbidities, surgical complications, length of stay, and pain medications will be obtained for each participant from the time of surgery. At 4-6 weeks postoperatively, parents or guardians will be asked to complete a survey at their follow-up appointment or online using Research Electronic Data Capture (REDCap). The survey includes assessments of the time taken to return to school and work, return to full activity, surgical complications, and patient and caregiver satisfaction (**Figure 2**).

Figure 2. Postoperative Survey

Your Child's Experience Postoperatively	
For how long was your child on pain medications following the procedure?	 1-2 days  3-4 days  4-7 days  >1 week
How many days following the procedure did your child return to school, daycare, summer camp, or summer school?	
Approximately how many days after surgery did your child return to full activity (sports, gym, dance, outdoor play, etc.)?	
Did your child's wound have any oozing or bleeding following discharge from the hospital?	 None  Mild (slight drainage)  Moderate (drainage with blood)  Severe (oozing with blood)

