If your followed physician-directed instructions, did you follow the recommendations strictly?	 Yes  No  Somewhat
If you chose self-directed instructions, did you feel comfortable determining when your child was able to resume full activity?	 I felt comfortable  I had some concerns  I did not feel comfortable

Figure 2. Postoperative survey provided to patients 4-6 weeks following their procedure. Patients were able to complete the survey at their postoperative visit or online via REDCap.
	

Objectives

The primary outcome of this study is length of time to full activity.

Secondary outcomes will evaluate patient preference to PDAR and SDAR based on choice of study arm and the impact of restriction type on number of parental days off work.

Clinical complications will also be tracked. Patient satisfaction will be defined as a cumulative score of three satisfaction factors (child, parent, and satisfaction with discharge guidelines).

Statistical Analysis

Continuous data will be presented as mean (SD) or median (IQR) depending on distribution, and analyzed using unpaired t tests or Mann Whitney ranked sum tests. Categorical data will be presented as number (%) and will be analyzed using Chi Square or Fisher's exact test depending on frequencies P values <.05 will be considered significant.

REFERENCES

3. Pommergaard H-C, Burcharth J, Danielsen A, Angenete E, Haglind E, Rosenberg J. No consensus on restrictions on physical activity to prevent incisional hernias after surgery. *Hernia*. 2014;18(4):495-500. doi:10.1007/s10029-013-1113-8

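### Families choose their arm, but the child's usual activity and commitments in the first two weeks are not named among the data to be collected, and the primary comparison is unadjusted

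*Combined protocol and SAP*

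**What the plan says.** Allocation is by family preference. The Study Design summary states: "Participating families will choose to enroll in either the control (PDAR) or experimental (SDAR) groups". Under Objectives, "The primary outcome of this study is length of time to full activity". The Figure 2 survey, completed by the caregiver 4 to 6 weeks after surgery, measures it with the question "Approximately how many days after surgery did your child return to full activity (sports, gym, dance, outdoor play, etc".

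The two arms differ in what decides the day of return. Under Methods, Participants: "The PDAR instructions detailed that patients are restricted from full, normal activity for 2 weeks after their procedure". SDAR families are told that "they may return to full activity when their pain is improving and the parent, or guardian, feels comfortable advancing their activity".

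On data to be collected, Methods, Data Collection has one sentence on items other than the survey: "Baseline characteristics, comorbidities, surgical complications, length of stay, and pain medications will be obtained for each participant from the time of surgery". The baseline characteristics are not itemised. The same section describes the survey: "The survey includes assessments of the time taken to return to school and work, return to full activity, surgical complications, and patient and caregiver satisfaction". Every question is reproduced in Figure 2. No question covers activity before surgery, events scheduled after it, or the reason for choosing an arm.

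Statistical Analysis provides unpaired t or Mann-Whitney tests for continuous data. It mentions no covariates, stratification, matching or weighting.

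**The concern.** How much sport and active play a child did before surgery is the pre-treatment counterpart of the primary outcome. A family whose child trains regularly, or has a match or class within two weeks, has an evident reason to prefer the arm without a fixed restriction. The same child may well return sooner whatever the instruction. The Background section itself notes that restrictions may affect extracurricular activities and that limiting children's activity is hard.

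If such children collect in SDAR, an earlier mean return there could arise even if the instruction did nothing. A larger sample does not help: it narrows the interval around a biased difference.

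This goes beyond the absence of an adjusted model. A model can be added at analysis, but only for variables on file. A factor that was never recorded cannot be adjusted for directly.

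**Working it through.** **No figure to reproduce.** The documents give no sample size, SD, expected difference or split between arms. What follows shows what such a bias could look like. It does not estimate it.

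**From the documents:** arm chosen by the family; outcome in days; unadjusted two-group test; significance at p < .05 (sidedness not stated, taken as two-sided).

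**Assumed:** half the children are regularly active; outcome SD is 5 days; the instruction has no effect; active children return g days earlier in either arm; active children choose SDAR with probability a and other children with probability b; N = 100 or 300 in total.

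**Formulas**

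- Active share in SDAR = a/(a + b); in PDAR = (1 − a)/(2 − a − b).
- Spurious difference B = g × (SDAR share − PDAR share).
- SDAR fraction of the sample = (a + b)/2, which is 0.60 in every scenario.
- SE = 5 × √(1/n_SDAR + 1/n_PDAR).
- Chance of p < .05 with no true effect = Φ(B/SE − 1.96) + Φ(−B/SE − 1.96).

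**Middle scenario (a = 0.75, b = 0.45, g = 3)**

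- Shares: 0.75/1.20 = 0.625 and 0.25/0.80 = 0.3125, a difference of 0.3125.
- B = 3 × 0.3125 = 0.94 day.
- N = 100: SE = 5 × √(1/60 + 1/40) = 1.02; B/SE = 0.92; chance 15.1%.
- N = 300: SE = 5 × √(1/180 + 1/120) = 0.59; B/SE = 1.59; chance 35.6%.

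**All scenarios**

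| a, b | g (days) | Active share, SDAR / PDAR | B (days) | N = 100 | N = 300 |
|---|---|---|---|---|---|
| 0.70, 0.50 | 2 | 0.583 / 0.375 | 0.42 | 6.9% | 10.9% |
| 0.75, 0.45 | 3 | 0.625 / 0.3125 | 0.94 | 15.1% | 35.6% |
| 0.80, 0.40 | 4 | 0.667 / 0.25 | 1.67 | 37.2% | 80.7% |

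**Check with other assumptions.** With equal arms, SD 5 and 100 per arm, a bias of 0.6 day gives p < .05 in 13.6% of trials and a bias of 0.8 day in 20.5%. For 0.8 day the figure is 12.6% with 50 per arm and 36.0% with 200 per arm. The pattern is the same.

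**Two things that would shrink the bias**

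1. *Recorded proxies.* If procedure, age or season accounted for half the imbalance, a 0.6-day bias would fall to 0.6 × 0.5 = 0.3 day: reduced, not removed.
2. *Compliance in PDAR.* Suppose a fraction c of PDAR children would return on the same day, around day 14, however active they are, with c unrelated to activity. For the effect among families who chose SDAR, the bias becomes (1 − c) × B. With c assumed to be one half, the middle scenario falls from 0.94 to 0.47 day. With c = 1 this confounding disappears for those families, and the result applies to them only.

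**The case against.** Several parts of the opposing case stand.

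*Are the variables certainly not collected?* A reader might infer that from their absence. The documents do not support it, because baseline characteristics are never itemised and could include them. The supportable statement is that they are not named. The survey is different: it is reproduced in full, and they are not in it.

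*Could no adjustment help?* A reader might infer this too, but it is too strong. Procedure is known, age is an eligibility criterion for both operations, and date of surgery may be recorded. All are plausibly related to sport and could take out part of the bias. There is no ground for expecting them to take out all of it.

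*Is the primary question unanswerable?* The stated aim is to compare time to full activity and to describe family preference. Choice of arm is itself a secondary outcome, so self-selection is deliberate. A descriptive comparison of the groups that chose each arm remains possible. What is not secure is reading the difference as an effect of the instruction.

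*Does the two-week restriction limit the mechanism?* To the extent that PDAR families comply, prior activity cannot bring their return forward, and the scenarios above ignore this. The survey asks about adherence twice, so the point can be partly examined. It does not dispose of the concern: compliance may be incomplete, and less active children may return after day 14.

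*Are the magnitudes evidence?* No. Prevalence, choice probabilities, shift, SD and sample size are all assumed, and so is the direction. The documents do not say which families prefer which arm. The figures show that the bias is possible, not that it is likely or large.

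*Is this a symptom of a wider gap?* In part. With no adjustment planned, even procedure goes unhandled, and other influences such as parental caution would remain after these two items are added. But data not collected cannot be supplied later by a better model, so the collection gap needs its own remedy.

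**Conclusion.** The point holds in limited form. The arm is self-selected, two plausible common causes of arm choice and day of return are named in neither the baseline list nor the survey, and the primary comparison is unadjusted. A difference in time to full activity may therefore partly reflect who chose SDAR.

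Size and direction cannot be derived from the documents. The assumed scenarios give 0.4 to 1.7 days. With no true effect they give a chance of p < .05 between 7% and 37% at N = 100, and between 11% and 81% at N = 300. These figures assume SD 5 days, half the children active, 60% choosing SDAR, and the same shift in both arms. PDAR compliance or recorded proxies would lower the bias.

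This should be changed, with medium confidence. If the baseline characteristics already include both items, listing them and adding the adjusted analysis is enough.

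**What to change.** Methods, Participants says enrolment is still accruing, so a change can still help.

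1. **Families enrolled from now on:** ask two items before the arm is chosen: (a) usual days per week of sport, gym, dance or vigorous play in the month before surgery; (b) whether a game, class or event is scheduled in the first two weeks after surgery.
2. **Data Collection:** itemise the baseline characteristics, including these two items, procedure and age.
3. **Statistical Analysis:** report both items by arm. Add one pre-specified regression of time to full activity on arm, the two items, procedure and age, stating its form in advance. Describe the result as an association among self-selected groups.
4. **Families already enrolled:** recalled answers may be requested, but use them only in a sensitivity analysis. They are given after the arm, and often the outcome, is known, and recall may differ by arm.

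Cost: two short questions and one regression model that the plan does not now contain, with no added procedure or visit. Data for children already enrolled will be recalled or missing, and confounding by factors other than these two will remain.

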If you answered mild, moderate, or severe to the previous question, when did this occur?	
If you answered mild, moderate or severe to the previous question, did this require any treatment by your surgical team?	
Did your child experience any postoperative complications?	 No  Yes
If you answered yes to the previous question, please specify:	
After resuming full activity, did your child experience an increase in pain?	 No  Yes
If you answered yes to the previous question, did they require any medication for the pain?	 No  Yes
How compliant was your child with their postoperative instructions?	 Compliant  Partially compliant  Not compliant

Postoperative Activity Restrictions in Children After Routine Surgery

5

How would you describe your child's overall satisfaction following the procedure?	 Very satisfied  Satisfied  Neither satisfied or dissatisfied  Dissatisfied  Very dissatisfied
Your Experience Postoperatively	
What is your relationship to the child?	 Mother  Father  Grandparent  Legal Guardian  Other
Did you or another caregiver take time off work to care for your child following their procedure?	 Yes  No
Did you have to find additional childcare for your child following their procedure?	 Yes  No
How would you describe your overall satisfaction following your child's procedure?	 Very satisfied  Satisfied  Neither satisfied or dissatisfied  Dissatisfied  Very dissatisfied
Were you satisfied with the instructions detailed in your discharge guidelines?	 Very satisfied  Satisfied  Neither satisfied or dissatisfied  Dissatisfied  Very dissatisfied

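### The survey's pain-medication duration answers overlap at day 4 and offer no answer for a child who took none; this affects the description of that item, not the primary outcome.

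*Combined protocol and SAP*

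**What the plan says.** The first item of the postoperative survey (Figure 2) reads "For how long was your child on pain medications following the procedure". The tick-box answers are 1-2 days, 3-4 days, 4-7 days and >1 week. They print intact and in order, so nothing suggests text lost from the page.

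One other survey item concerns pain medication. It follows a question about increased pain once full activity has resumed: "If you answered yes to the previous question, did they require any medication for the pain", answered No or Yes. It does not measure duration.

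Outside the survey, the Data Collection section states that "length of stay, and pain medications will be obtained for each participant from the time of surgery". It does not say whether duration, or use at home, is recorded.

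The Objectives section states: "The primary outcome of this study is length of time to full activity". It continues: "Secondary outcomes will evaluate patient preference to PDAR and SDAR based on choice of study arm", and adds parental days off work. Complications are tracked and a satisfaction score is defined. Pain-medication duration is not mentioned there.

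The Statistical Analysis section gives one general rule for items of this kind: "Categorical data will be presented as number (%) and will be analyzed using Chi Square or Fisher's exact test", according to frequencies, with "P values <.05 will be considered significant". It has no rule for placing a 4-day answer or for coding a child who took nothing.

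**The concern.** A set of tick-box answers should give each possible value one place and only one. This set fails in two ways. Two adjacent bands share day 4, and the lowest band starts at day 1, so a child given no medication has no true answer. The same form does offer None for wound oozing, so a zero answer is provided elsewhere but not here.

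The chi-square or Fisher's exact test that the plan would apply needs mutually exclusive categories. With an overlap, the split between 3-4 and 4-7 days depends partly on how each caregiver resolves day 4. Families choose their own arm, so the two arms need not resolve it in the same way. With no zero answer, a blank can mean no medication or no response, and a tick at 1-2 days can mean one or two days or none.

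At stake is the accuracy of the reported pain-medication durations and of any comparison of them between arms. This is the survey's only measure of that duration.

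**Working it through.** The document gives no figure to reproduce on this point. The check is a count of how many printed answers contain each whole-day duration, reading >1 week as 8 days or more. A sound set gives exactly one match for every day. The last column applies the same count to the replacement set None / 1-2 / 3-4 / 5-7 / more than 7 days.

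| Days on medication | Printed answers that contain it | Count | Count in replacement set |
|---|---|---|---|
| 0 | none | 0 | 1 |
| 1, 2 | 1-2 | 1 | 1 |
| 3 | 3-4 | 1 | 1 |
| 4 | 3-4 and 4-7 | 2 | 1 |
| 5, 6, 7 | 4-7 | 1 | 1 |
| 8, 9, 10 | >1 week | 1 | 1 |

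So one value is covered twice (day 4) and one is not covered at all (day 0). The boundary between 4-7 days and >1 week is clean in whole days.

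Next, what the overlap could do to a comparison. Let *q* be the share of children whose true duration is exactly 4 days, the same in both arms. Let *a* and *b* be the fractions of those children ticked as 3-4 days in the two arms. If the arms are otherwise identical, the observed difference in the 3-4 day percentage is

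*q* × (*a* − *b*),

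and the difference in the 4-7 day percentage is the same size with the opposite sign. The largest value is *q*, reached when *a* = 1 and *b* = 0. The document gives neither *q* nor *a* and *b*. Purely as an assumption, *q* = 5%, 10% or 20% gives a ceiling of 5, 10 or 20 percentage points. These are bounds under the most extreme split, not estimates. If both arms resolve day 4 alike (*a* = *b*), the difference is zero.

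Merging the two bands removes this effect. The 3-7 day share contains every 4-day child whichever box was ticked, so *a* and *b* drop out.

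Merging does nothing for day 0. On the printed form a zero-day child is either blank or in 1-2 days, and the survey alone cannot identify the child in either place.

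**The case against.** The strongest case against the point is that no stated outcome uses this item. The Objectives section does not name it, and the Data Collection summary of what the survey assesses covers school and work, activity, complications and satisfaction, but not pain medication. That stands, and it limits the point to a descriptive or between-arm summary of one item.

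Several stronger readings are tempting, and the document does not support them.

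- A reader might infer that the primary comparison is damaged, because SDAR families are told "they may return to full activity when their pain is improving". That instruction turns on improving pain and caregiver comfort, not on stopping medication. Time to full activity is a separate open question in days. The Statistical Analysis section has no model that uses medication duration to explain it.
- A reader might infer that the item is uncodable throughout. It is not: days 1 to 3 and 5 onward each have one place. A 4-day child ticked in either band is in a band that truly contains day 4, so the answer is ambiguous rather than false. Only a zero-day child ticked as 1-2 days is misclassified.
- A reader might take the item to concern treatment after discharge. It asks about the period following the procedure, so a child medicated only in hospital can truthfully be ticked at 1-2 days. The zero-day group may therefore be small.
- A reader might expect the pain-medication data collected from the time of surgery to separate no medication from no response. The document does not say that those data cover home use or duration, so this cannot be relied on.

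It is also fair to say that answers recalled at 4-6 weeks may be imprecise by a day anyway. That lowers the practical weight of the day-4 overlap, but it is no reason to keep answers that overlap, and it does not bear on the missing zero.

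**Conclusion.** The defect is real and minor. As printed, the answers overlap at exactly one value (4 days) and omit one (0 days), and no other text repairs either. The count assumes whole days and that >1 week means more than 7 days.

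The effect is limited to describing or comparing pain-medication duration. The primary outcome is unaffected, and so are the named secondary outcomes.

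The share of children affected cannot be quantified: the document gives no distribution of medication duration and no share of children who took none. Any percentage put on it would be an assumption. What can be said is that a spurious difference between arms from the overlap cannot exceed the share of children at exactly 4 days, if that share is the same in both arms.

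**What to change.** For forms still to be completed, replace the answers with None / 1-2 / 3-4 / 5-7 / more than 7 days, or ask for the number of days with 0 allowed. Either gives every whole day one place. The Participants section says that recruitment is still open and the survey can be completed in REDCap, so this is an edit to one item, carried over to the form used at the follow-up visit.

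For forms already returned, merge 3-4 and 4-7 into a single 3-7 day band. State in the report that blanks and 1-2 day answers on those forms may include children who took no medication.

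The cost is small. Old and new forms can be pooled only at the coarser 3-7 day band, and the boundary between none and 1-2 days stays uncertain on the old forms.

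### The primary-outcome item has no defined answer for a child not yet back to full activity at the single 4-6 week survey, so some of the longest times may be left out; probably a small effect, and cheap to close

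*Combined protocol and SAP*

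**What the plan says.** The Objectives section states: "The primary outcome of this study is length of time to full activity". The Summary names the source: "caregivers will complete a survey to assess time to resume full activity". Data Collection gives the timing: "At 4-6 weeks postoperatively, parents or guardians will be asked to complete a survey", at the follow-up appointment or online. No later contact is described.

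In the Postoperative Survey (Figure 2) the item is "Approximately how many days after surgery did your child return to full activity (sports, gym, dance, outdoor play, etc", followed by a blank entry. No response for a child who has not returned is printed. A later item, "After resuming full activity, did your child experience an increase in pain", offers only No or Yes.

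Statistical Analysis reads: "Continuous data will be presented as mean (SD) or median (IQR) depending on distribution", "analyzed using unpaired t tests or Mann Whitney ranked sum tests". It has no rule for a child not yet back or for a missing answer.

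Two further statements bear on size and remedy. Under the PDAR instructions, "patients are restricted from full, normal activity for 2 weeks after their procedure". The self-directed (SDAR) instructions set no upper limit and leave the timing to improving pain and the family's comfort. The document says both that recruitment continues (Participants) and that it reports preliminary results (end of Background and Significance).

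**The concern.** A child who has not resumed full activity by the survey has, by definition, one of the longest times in the study. The caregiver of that child meets a question that cannot be answered as worded. If the field is left blank, the record looks the same as a skipped question and would most naturally be treated as missing. The chance of being lost would then depend on the outcome itself, and analysts could not repair or count the loss afterwards.

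An arm that loses its slowest children looks faster than it is. If the shares lost differ by arm, the arm difference is biased, and the direction depends on which arm loses more. Equal shares cannot be assumed, because families choose their arm and the two sets of instructions differ. Nothing in the plan asks for the number not yet back to be reported, so a reader could not judge whether this happened.

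**Working it through.** The plan states no sample size, spread, expected time or share not back, so there is no figure of its own to reproduce. The size can only be illustrated.

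**Inputs from the documents.** Survey at 4-6 weeks, that is day 28-42. PDAR restriction of 2 weeks, ending on day 14. The survey therefore falls 28 − 14 = 14 to 42 − 14 = 28 days after it ends.

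**Assumptions.** Log-normal times T; median 14 days in PDAR (set to the length of the restriction) and 10 days in SDAR, so the true median difference is 4.0 days; log-SD s varied; survey day C spread evenly over day 28-42; a child with T > C is left out.

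**Formulas.**
- P(C ≥ t) = 1 for t ≤ 28, (42 − t)/14 for 28 < t < 42, and 0 afterwards.
- Observed density w(t) = f(t) × P(C ≥ t). Share not back q = 1 − ∫w. The median of those left in is the half-point of w.
- Probability that a PDAR child takes longer than an SDAR child (the quantity behind the Mann-Whitney test), with I = ∫ w_PDAR(t) W_SDAR(t) dt, where W is the running integral of w:
  - all true times: Φ(ln 1.4 / √(s_S² + s_P²)), since 14/10 = 1.4
  - not-back children left out: I / [(1 − q_S)(1 − q_P)]
  - not-back children kept as tied worst ranks: I + q_P(1 − q_S) + ½ q_P q_S

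**One row in full (s = 0.5 in both arms).** q_S = 0.0076, q_P = 0.0383, I = 0.6447.
- True: Φ(0.3365/0.7071) = Φ(0.476) = 0.683.
- Left out: 0.6447/(0.9924 × 0.9617) = 0.676.
- Tied worst ranks: 0.6447 + 0.0383 × 0.9924 + 0.5 × 0.0383 × 0.0076 = 0.683.

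**All six cases.**

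| log-SD SDAR / PDAR | not back SDAR / PDAR | median difference left in (true 4.0) | probability: true → left out |
|---|---|---|---|
| 0.3 / 0.3 | 0.0% / 0.2% | 13.988 − 10.000 = 3.99 | 0.786 → 0.786 |
| 0.4 / 0.4 | 0.1% / 1.5% | 13.898 − 9.993 = 3.91 | 0.724 → 0.721 |
| 0.5 / 0.5 | 0.8% / 3.8% | 13.668 − 9.952 = 3.72 | 0.683 → 0.676 |
| 0.6 / 0.6 | 2.1% / 6.8% | 13.297 − 9.845 = 3.45 | 0.654 → 0.643 |
| 0.8 / 0.8 | 6.2% / 13.0% | 12.278 − 9.400 = 2.88 | 0.617 → 0.601 |
| 0.8 / 0.3 | 6.2% / 0.2% | 13.988 − 9.400 = 4.59 | 0.653 → 0.695 |

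With tied worst ranks, the probability is within 0.001 of the true value in every row; the largest gap is 0.6165 against 0.6169. Every not-back child has T > 28, above both medians, so ranking these children last also restores the medians to 14 and 10.

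**How plausible is log-SD 0.8 in PDAR?** It implies Φ(ln(8/14)/0.8) = Φ(−0.70) = 24% back by day 8 despite the restriction, and 1 − Φ(ln(52/14)/0.8) = 1 − Φ(1.64) = 5% still not back at day 52.

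**Means.** At s = 0.5 the true mean difference is (14 − 10) × exp(0.125) = 4.53 days; with not-back children left out it is 3.73. Means are more sensitive than medians.

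**Other medians.** With medians of 15 and 10 (true difference 5.0) and a fixed cut at day 42, the difference is 4.96 at log-SD 0.4 and 3.95 at 0.8. With a fixed cut at day 28, the earliest day in the window, it is 4.59 and 2.98. The pattern is the same.

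**The case against.** The best answer to this point is that the harm is conditional and probably small. The procedures are routine hernia repair and appendectomy for uncomplicated appendicitis, and the survey comes 2-4 weeks after the PDAR restriction ends. At log-SD 0.3-0.5 the Mann-Whitney probability moves by at most 0.007. The larger effects need a spread that fits poorly with an instruction that should cluster PDAR returns at or after day 14, and the reversed case has no support in the documents either. All of this stands, and it is why the point is minor.

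An open field may also draw 'not yet', a guessed day or the survey day, so being left out is only one possible result. That stands too: the calculation models complete exclusion only. But no coding is stated for any of these answers, and a blank remains ambiguous.

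The mean-based shift carries little weight, because the plan chooses between mean and median by distribution and skewed data should lead it to medians. That is fair.

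Finally, preliminary results are already mentioned, so a rule written now comes after early data were seen. This does not remove the need for the rule, but the change has to say so.

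A reader might infer more: that the planned tests are unsuitable, that time-to-event methods are required, or that the comparison is already biased. The documents do not support this. The Mann-Whitney test can use a child known only to be slowest. What is missing is a response option and a coding rule. No passage shows how many children are affected, or in which arm.

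**Conclusion.** The gap is real and minor. The primary outcome depends on an item that a child not yet back cannot answer as worded, with no later contact and no coding rule, so some of the longest times may be left out without trace. The size cannot be established from the documents. On the stated assumptions it is negligible for medians and ranks at narrow to moderate spreads. It becomes material only at wide spreads: at log-SD 0.8 in both arms the median difference shrinks to 2.88 days, and with a wide SDAR and narrow PDAR spread it grows to 4.59, against a true 4.0. No direction of bias can be asserted. The case for acting rests on the low cost and on making the number affected visible.

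**What to change.** - **Form.** Add a 'not yet returned to full activity' box to the item, and record the survey completion date.
- **Analysis section.** State that children with this box ticked stay in the primary comparison as tied worst ranks in the planned Mann-Whitney test, that medians are reported, and that the number not yet back is given by arm. Censoring at the survey date is an optional alternative.
- **Data already collected.** Date the rule as added after early data were seen. Check earlier blank and free-text answers. For participants surveyed on the old form, show the result twice: with unresolved blanks left out, and with them ranked worst.
- **Optional tidying.** Add 'not applicable' to the pain item that presumes return. No stated analysis depends on it.

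The cost is one tick box, one date field if it is not already captured, a few sentences and a check of past surveys, which is feasible while recruitment continues. The downsides are that two form versions are pooled and that a mean is no longer reported for the primary outcome. Because survey days vary, a child not back at day 28 would also rank behind one who returned at day 40; in the six cases above this cost no more than 0.001 in probability.
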